Aim 1. Determine the effect of sleep extension on whole-body, multi-organ and cellular metabolic function in MU adults. We hypothesize that sleep extension implemented at home in people who chronically maintain short sleep schedules will: i) improve *in vivo* insulin sensitivity in the liver, adipose tissue and muscle; ii) have beneficial effects on 24h plasma insulin (concentration, secretion and clearance) glucose, and FFA profiles; iii) decrease intrahepatic triglyceride content; and iv) alter specific plasma metabolites (assessed every 6h for 24h) that are known to be associated with insulin resistance and the development of T2D.

In addition, untargeted metabolomics analyses will be performed to help identify novel metabolites associated with sleep extension-induced improvement in metabolic function that will serve as the basis for future investigation of these specific metabolites/bioactives.

Aim 2. Determine the effect of sleep extension on purported mechanisms responsible for metabolic dysfunction induced by obesity or sleep restriction: i) misalignment between the master clock of the suprachiasmatic nucleus (assessed by 24h plasma melatonin rhythm) and peripheral circadian clocks (assessed by serial measurements of peripheral blood mononuclear cell [PBMC] gene expression); ii) oxidative stress (urinary 8-iso-prostane F2 α , plasma oxysterols and glutathione-to-oxidized glutathione ratio, and adipose tissue protein carbonylation); and iii) systemic and adipose tissue inflammation (proinflammatory cytokines and prostanoids). We hypothesize that sleep extension will: i) improve alignment between central and peripheral rhythms; ii) reduce oxidative stress; and iii) decrease plasma and adipose tissue markers of inflammation.

We will test these hypotheses by: i) a one-stage hyperinsulinemic-euglycemic clamp (HEC) procedure plus stable isotope tracer infusions; ii) 24h urine collection iii) hourly blood sampling for 24h; iv) muscle and adipose tissue biopsies; and v) magnetic resonance imaging.

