Metabolomics. State-of-the-art mass spectrometry techniques will be used to measure specific circulating metabolites that have been linked with metabolic dysfunction and/or sleep restriction, including markers of inflammation, oxidative stress, and insulin resistance (see section **D2.2.1**). These metabolites will be evaluated in blood samples obtained every 6h for 24h to provide an integrated assessment of plasma concentrations throughout the day. Additionally, we will measure a key marker of oxidative stress in a 24h urine collection (urinary 8-iso-prostane F2 α)^{62,63}. To capture these metabolites of interest, multiple complementary LC methods will be performed as previously described^{62,63}, each optimized to capture a chemical subset of the metabolome, and coupled to a high resolution Thermo Orbitrap QExactive mass spectrometer. This orthogonal chromatography will include hydrophilic interaction liquid chromatography (HILIC) using a Sequent Zic-pHILIC HPLC column to capture polar metabolites, reverse phase chromatography using a superficially porous Phenomenex Kinetex C18 UPLC column to capture lipids and peptides, and weak ion exchange chromatography using a Phenomenex Luna aminopropyl HPLC column to capture sugars, nucleotides, and phosphates. Metabolites of interest are definitively identified by using MS/MS analysis, with matching of LC measures and MS/MS fingerprint to commercial metabolite standards. In addition to targeted measures, simultaneous untargeted metabolomics analyses will be performed to comprehensively identify novel metabolites that may be associated with sleep related improvement in metabolic function. These metabolite markers will serve as the basis for future investigation and potentially enable discovery of novel metabolite biomarkers and bioactives involved in improved metabolic function induced by sleep extension in persons with MUO.

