D4.1. Data analyses. Statistical evaluation of the study data will be conducted in collaboration with [name], a biostatistician in the Washington University Institute of Clinical and Translational Sciences (ICTS) Research Design & Biostatistics Group. We will use a modified intention-to-treat (mITT) analysis, in which all subjects that complete the study will be analyzed regardless of their adherence to the assigned sleep intervention (i.e., continued short sleeping pattern in the control group and successful sleep extension [adding ~2 h of time-in-bed per night ensuring at least 7h/night] in the sleep extension group). Analysis of covariance (ANCOVA) with the post-treatment value as the dependent variable will be used to determine whether there are between group differences in our metabolic outcomes assessed during the HEC procedure and 24-h blood sampling study with the pre-intervention value used as a covariate. Characteristics at baseline between groups will be compared by using t-tests or Wilcoxon's test for continuous variables and chi square tests for dichotomous variables; any significant differences between groups will be used to adjust subsequent statistical analyses when necessary. Violations of the assumption of homogeneity of variance and/or sphericity will be corrected, if necessary, via transformation of data to produce data that satisfy normality and equal variance assumptions^{90,121-123}. As this protocol incorporates a 2-time point, pre-post study design there is no basis to input follow-up data when only baseline data are available. Because of this limitation, we will compare characteristics between completers and non-completers by using t-tests or Wilcoxon's test for continuous variables and chi square tests for dichotomous variables; these results will be reported in addition to the ANCOVA analysis. Metabolite analyses will be performed by using an ANOVA and Tukey post-hoc testing for statistical significance between conditions and across time. For discovery based untargeted metabolomics analysis, a conservative statistical threshold will be applied at the outset (Bonferroni corrected P value of $<10^{-5}$ to account for multiple hypothesis testing). To further minimize false discovery, we will also use principal component analysis as well as sparse partial least squares and LASSO regression with internal cross-validation. Metabolites identified using these methods will be prioritized for future investigation as potential mechanisms underlying sleep related metabolic improvements.

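### The untargeted metabolomics aim concerns metabolites linked to metabolic improvement, but no specified analysis relates a metabolite to a metabolic outcome, so metabolites that only respond to the sleep change could be prioritised as mechanisms

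*Combined protocol and SAP*

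**What the plan says.** Section A, Aim 1, gives the purpose: "untargeted metabolomics analyses will be performed to help identify novel metabolites associated with sleep extension-induced improvement in metabolic function". Section D2.5 (Metabolomics) repeats it: the untargeted work is to "comprehensively identify novel metabolites that may be associated with sleep related improvement in metabolic function".

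Section D4.1 gives the analysis. The test is described in one sentence: "Metabolite analyses will be performed by using an ANOVA and Tukey post-hoc testing for statistical significance between conditions and across time". For untargeted features "a conservative statistical threshold will be applied at the outset", namely a Bonferroni-corrected P below 10^-5. Then, as a further guard against false discovery, "we will also use principal component analysis as well as sparse partial least squares and LASSO regression with internal cross-validation". The hits are put to this use: "Metabolites identified using these methods will be prioritized for future investigation as potential mechanisms underlying sleep related metabolic improvements".

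D4.1 names no response variable for sparse PLS or LASSO. It does not say whether a metabolite must pass every method or any one. It states no model relating metabolite change to change in glucose Rd, 24-h AUC or another metabolic outcome.

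**The concern.** The aim and the stated test address different null hypotheses. For the aim, the null is that a metabolite's change is unrelated to the change in metabolic function. For the ANOVA, it is that the metabolite's mean is the same across conditions and times. Rejecting the second shows a response to the intervention and says nothing direct about the first. Changing the P cut-off does not alter which hypothesis is tested.

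This matters here because the intervention alters more than sleep duration. Section D2.3 also changes bed and wake times and asks participants to reduce light at night and increase it in the morning. Section D2.2.1 times blood sampling from waking. Metabolites governed by the clock, light or sleep itself could differ by arm without any role in insulin action.

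Two errors are possible. Markers of sleep exposure could be carried forward as mechanisms, and nothing in D4.1 makes that label depend on Rd having improved. Conversely, a metabolite that closely tracks improvement but differs only modestly between arms could be passed over. The list is meant to direct later work, so either error would misdirect it.

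**Working it through.** **The plan's own figure.** There is no power or sample-size figure for metabolomics. The nearest is D4.2.1: Rd difference 7.9, SD 6.4, 15 per group. The standardised effect is 7.9/6.4 = 1.234, and a two-sided two-sample t-test at 0.05 has power 0.904 by noncentral t. The 15 per group reproduces. It does not bear on the metabolomics aim, but 1.234 is used in step 3.

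**Inputs.** From the documents: 25 per arm (D2.3) and P<10^-5 (D4.1). Assumed, because the documents give none: arm shift d of a metabolite in SD units, and its within-arm correlation r with the change in Rd. A two-sample t-test on metabolite change stands in for the ANOVA contrast between conditions.

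**Model.** Metabolite change = r·z + √(1−r²)·e + d·arm, and Rd change = z + δ·arm, with z and e independent standard normal. The arm screen has noncentrality d·√(n/2) = 3.54·d on 48 df. The association test is the partial correlation of the two changes given arm, on 47 df. Its rejection rate does not depend on d or δ.

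**Step 1: unlinked metabolite** (r=0, no Rd effect), 25 per arm.

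| Shift d | Arm screen, P<10^-5 | Arm-adjusted association, P<0.05 |
|---|---|---|
| 1.0 SD | 11% | 5% |
| 1.5 SD | 64% | 5% |
| 2.0 SD | 97% | 5% |

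At 15 per arm, shifts of 1.5 and 2.0 SD pass the screen in 16% and 55% of trials.

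**Step 2: linked metabolite** (Rd effect δ = 1), both tests at the plan's 10^-5, 25 per arm.

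| r | Shift d | Arm screen | Arm-adjusted association |
|---|---|---|---|
| 0.6 | 0.5 SD | 0.2% to 0.3% | about 58% |
| 0.6 | 0.75 SD | 2% | about 58% |
| 0.4 | 0.5 to 0.75 SD | 0.2% to 2% | about 5% |

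At r=0.3 the association test falls below 1%. With 22 completers per arm and r=0.6, the arm screen finds 0.2% to 1.3% and the association test 45% (3% at r=0.4). At a looser P<0.001 and r=0.6, the association test reaches 92% at 25 per arm, but that is not the plan's threshold.

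**Step 3: would correlating with Rd across all participants be enough?** Take r=0, d=2 and the planned Rd effect of 1.234. The expected pooled correlation is approximately [d/√(d²+4)]·[1.234/√(1.234²+4)] = 0.707 × 0.525 = 0.37; simulation gives 0.38. This unlinked metabolite is nominally associated with Rd (P<0.05) in 81% of trials. The arm difference alone creates the correlation, so arm must be in the model.

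**The case against.** The strongest reply is that D4.1 does not stop at ANOVA. Sparse PLS and LASSO are supervised methods. They need a response, and it could be Rd or another metabolic outcome. They may also be meant as a filter on the ANOVA hits, given their stated purpose of limiting false discovery. A reader might infer that the plan tests arm differences only, that unlinked metabolites *would* be prioritised, and that the discovery question goes unanswered. The documents do not support that: they are silent on the response and on how the methods combine, and silence supports *could*. The reply does not close the gap, however. If the response is arm, these methods ask the same question again. If it is Rd pooled over arms, step 3 shows that the two kinds of metabolite are still not separated.

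The component is also exploratory. Aim 1 says it will help identify candidates, and D4.1 calls them potential mechanisms for later work. A randomised arm contrast is a legitimate discovery screen. This limits the consequence. It does not justify a label that the screen cannot support.

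The figures rest on chosen shifts and correlations. That stands. At 10^-5 the association test is no near-certain detector: with 50 participants it has 80% power only for a correlation of about 0.65.

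Finally, an arm-adjusted association is observational. It uses within-arm variation, including that of controls who were not extended, so it does not by itself isolate improvement caused by sleep extension. Metabolic function in Aim 1 is also wider than Rd. Both points stand and shape the fix.

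**Conclusion.** The concern holds in this form: the aim is about association with metabolic improvement, the only test with a stated contrast uses no metabolic outcome, the supervised methods have no named response, and the hits are nonetheless prioritised as potential mechanisms. Metabolites that merely respond to the intervention could be so labelled, whether or not Rd improves, and outcome-linked metabolites with a modest arm difference could be missed.

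The sizes in the working show direction and order of magnitude under assumed shifts and correlations; they are not forecasts for this trial. The advantage of the association test at the plan's threshold is large only for strong within-arm correlations. The point affects an exploratory part of Aim 1 and leaves the primary and secondary outcomes untouched. It is still worth changing, because a more suitable analysis is available on data already being collected.

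**What to change.** In D4.1, replace the prioritisation sentence with two separately derived lists.

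1. Metabolites that differ by arm in the planned screen, labelled 'responsive to sleep extension'.
2. Independently of list 1, for each metabolite, regress post-intervention glucose Rd on the metabolite change with baseline Rd and arm in the model. Test two-sided, so that a fall accompanying better Rd also counts, with multiplicity adjustment. Label hits 'associated with metabolic function'. Other prespecified metabolic outcomes may be added.

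Name the same baseline- and arm-adjusted outcome as the response for sparse PLS and LASSO, and state how the methods combine.

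Prioritise as potential mechanisms of improvement only metabolites on both lists. Report those on list 2 alone as candidates, so that a modest arm difference does not remove them from view. Do not use the mechanism label if the primary Rd comparison shows no improvement.

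The cost is SAP wording and some extra analysis, with no new data. Fewer metabolites will carry the mechanism label, only strong associations will survive strict multiplicity control, and the association remains observational and hypothesis-generating.

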D2.3. Sleep extension intervention. After completing baseline testing, subjects will be randomized, stratified by sex, to either: 1) *sleep extension* for 4-6 wk (n=25) or 2) *continued habitual short sleep* for 4-6 wk followed by 4-6 wk *sleep extension* (n=25). Randomization will be accomplished using the online randomization module of REDCap, a secure, web-based application designed to support data capture for research studies¹⁰⁰. Permuted blocks with varying block sizes will be used to ensure that there is no temporal bias in group assignment. When randomization occurs, the study coordinator will enter the REDCap system and will be asked to respond to a series of questions establishing the eligibility of the subject. The randomization assignment will only be revealed if all eligibility criteria are satisfied. We chose a 6-wk sleep extension intervention, because the only published study that showed a potential benefit of sleep extension on metabolic function used a 6-wk sleep extension protocol⁴⁸. Sleep and circadian expert members of the research team will use the baseline assessments to develop an individualized targeted intervention for each subject randomized to the sleep extension group with the goal of increasing each subject's sleep schedule by ~2h/night to reach a minimum of 7h/night. We chose 7.0h/night as a cut-off for short sleepers, since it is the minimum recommendation from the American Academy of Sleep Medicine recommendation for our targeted age-range (i.e., 18-65 years old). Our preliminary data on sleep extension in this age-group demonstrate our ability to extend sleep by over 2h/night (Table 1, section **C2.5**).

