
D4.2. Sample size considerations. Using G*Power 3.1.9.2¹²⁴ we estimate that 15 participants/group will be required to detect *realistic and clinically meaningful effects of sleep extension* (based on data from our own studies evaluating weight loss or weight gain^{36,87,88} and to data from our own and other groups assessing the metabolic effect of sleep restriction^{17-19,24}) with >90% power using two-sided tests at the $\alpha=0.05$ level of significance in all primary and secondary outcomes listed below.

D4.2.1 Primary outcome

Insulin-mediated glucose Rd. We have found the average insulin-mediated glucose Rd during high-dose insulin infusion to be 59.1 $\mu\text{mol/kg FFM/min}$ in people with obesity with a day-to-day variability of 6.4 $\mu\text{mol/kg FFM/min}$ (mean \pm SD) ⁷⁶. Using this SD and assuming similar variance in the sleep restriction and extension groups, we estimate we will be able to detect a $\sim 7.9 \mu\text{mol/kg FFM/min}$ ($\sim 13\%$) difference between groups. This difference is smaller than the $\sim 20\%$ reduction in insulin-mediated glucose Rd observed after acute (1 to 7 d) sleep restriction^{17-19,24}.

D4.2.2 Secondary outcomes

24-h glucose area-under-the curve (AUC). We have found average 24h glucose AUC is 2650 mg/dl/24h in people with obesity with a day-to-day variability of $80 \pm 130 \text{ mg/dl/24h}$ (mean \pm SD). Using this SD and assuming similar variability in both groups, we estimate we will be able to detect a between group difference of $\sim 137 \text{ mg/dl/24h}$ ($\sim 5.2\%$). Five nights of sleep restriction increases average plasma glucose concentration by 11% over 10 h during the day¹²⁵. Two nights of sleep restriction increases postprandial breakfast plasma glucose AUC by 7.4% after breakfast¹²⁶.

24-h insulin AUC. We have found average 24-h insulin AUC is $818 \pm 333 \mu\text{U/ml/24h}$ in people with obesity with a day-to-day variability of $26 \pm 85 \mu\text{U/ml/24h}$ (mean \pm SD). Using this SD and assuming similar variability in both groups, we estimate we will be able to detect a between group difference of $\sim 90 \mu\text{U/ml/24h}$ ($\sim 11\%$). Five nights of sleep restriction increases average plasma insulin concentration by 29% over 10 h¹²⁵. Two nights of sleep restriction increases postprandial breakfast plasma insulin AUC by 52%¹²⁶.

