Tissue gene expression and markers of inflammation and oxidative stress. It is difficult to make robust estimates of our study power to detect changes in molecular outcomes in adipose tissue and PBMCs, because of limited data evaluating these variables and the unknown effects of extending sleep. However, in our own experience, the population variance in PBMC and adipose tissue gene expression is $\sim 30\%$ ^{36,87,88}. In those studies, we used real-time PCR methods and detected transcriptional changes after diet-induced weight gain or weight loss^{36,87,88}. Accordingly, we estimate that we have $\geq 80\%$ power to detect $\sim 35\%$ difference in gene expression outcomes between groups, with a two-sided p-value of <0.05 .

D5. Scientific Rigor.

We have made every effort to ensure we obtain robust results: i) the hypotheses being tested in this proposal are based on a sound foundation of preliminary data from our own studies and results from other studies; ii) we will use a randomized controlled study design, and well-established and validated techniques to obtain the study outcomes; iii) a carefully-defined population (metabolically unhealthy with strict exclusion criteria to remove factors known to influence outcomes) will be enrolled in the study; iv) we provide packed-out meals for 3 days before each inpatient study and provide standardized meals during admission to reduce variability; v) treatment groups will be balanced with regards to sex; and vi) the sample size has the statistical power needed to detect meaningful treatment effects.

D6. Timeline.

We plan to complete all inpatient studies within the first 4.5 years to leave time for final sample processing and data analyses in the last 6 months of the grant period (Table 2). This schedule will accommodate the time required to initiate the study, recruit and screen subjects, perform the experimental protocols before and after subjects complete the sleep extension intervention, process and analyze the study samples, collate the data, finalize the data analyses, and write manuscripts.

Table 2. Study timetable

	Subjects complete Admission 1 studies (baseline) (n)	Subjects complete Admission 2 studies (baseline) (n)	Subjects complete Admission 3 studies (post-intervention) (n)	Subjects complete Admission 4 studies (post-intervention) (n)
Year 1	9	9	5	5
Year 2	13	13	13	13
Year 3	13	13	13	13
Year 4	13	13	13	13
Year 5	2	2	6	6
Total	50	50	50	50

D7. Special considerations

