
D7.2 Facilities for conducting sleep studies. The PI ([name]) is Director of the Clinical Research Unit, which now houses a newly-constructed, state-of-the-art sleep laboratory that coordinates services (certified polysomnographic technicians and equipment maintenance) with the Washington University Sleep Medicine Center. The CRU sleep laboratory was designed with direct and comprehensive input from the Co-Is of this proposal, [name], [name] and [name]. The sleep laboratory is comprised of a 170 sq. ft. temperature-, sound- and light-controlled sleep study room which is equipped with a Compumedics Grael PSG/EEG system with video monitoring. A control room with a dedicated computer for PSG review and processing is located just outside the sleep study room. A sound-insulated, light-proof catheter portal passes from the control to the sleep study room which allows blood sampling without entering the room and infusion of tracers and hormones with the infusion pump located in the control room to eliminate infusion pump noise at the bedside. The sleep study room is connected via intercom to the control room and the CRU nurses station. A shared software license is available for off-site sleep scoring and two Alice PDx Portable sleep diagnostic systems (Philips Health) are available for off-site or home sleep monitoring.

D7.3 Compliance with sleep extension and attrition. We recognize the potential risk of attrition in this long duration sleep extension outpatient study. Therefore, we have developed a specific strategy to help ensure compliance with the sleep extension protocol that is described in section **D2.3**. Moreover, our Co-Is at UCB have shown that successful sleep extension is possible (see preliminary data in section **C2.5**) with good compliance and minimal drop-outs (only 1 of 15 subjects was not compliant with the sleep extension protocol and was removed from the study). In addition, the research coordinators who will be involved in the present proposal have demonstrated considerable success in retaining study participants in previous studies (>90%) that involved rigorous long-term lifestyle intervention (diet-induced weight loss and weight gain, and exercise training) with even more complex metabolic assessments e.g., 36,87,88,127,128.

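### The 24-h glucose and insulin AUC differences in D4.2 have about 80% power at 15 per group, not more than 90%; they need 20 per group for 90%.

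*Combined protocol and SAP*

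**What the plan says.** D4.2 of the combined protocol and SAP opens with one general claim, calculated in G*Power: "we estimate that 15 participants/group will be required to detect" realistic and clinically meaningful effects, "with >90% power using two-sided tests at the" 0.05 "level of significance in all primary and secondary outcomes listed below". D4.2.1 and D4.2.2 then give an SD and a detectable difference for three outcomes:

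- **Insulin-mediated glucose Rd (primary):** SD 6.4, difference about 7.9 µmol/kg FFM/min (about 13% of 59.1).
- **24-h glucose AUC (secondary):** day-to-day variability 80 ± 130, difference about 137 mg/dl/24h (about 5.2% of 2650).
- **24-h insulin AUC (secondary):** day-to-day variability 26 ± 85, between-person SD 333, difference about 90 µU/ml/24h (about 11% of 818).

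Each AUC difference is introduced by the same sentence: "Using this SD and assuming similar variability in both groups, we estimate we will be able to detect a between group difference of" the figure quoted. No other group size or power is attached to it. The last paragraph of D4.2.2 claims at least 80% power for a difference of about 35% in molecular outcomes: "difference in gene expression outcomes between groups, with a two-sided p-value of" less than 0.05.

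D2.3 randomises 25 per group. D4.1 plans the comparison differently from a t-test: "Analysis of covariance (ANCOVA) with the post-treatment value as the dependent variable will be used to determine whether there are between group differences", with the pre-intervention value as covariate. D4.2 gives no baseline correlation and no allowance for attrition.

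**The concern.** D4.2 gives the group size, the power, the significance level, the SDs and the differences, so the claim can be checked. The standardised differences do not match each other: Rd is set at 1.23 SD and the two AUCs at about 1.05 SD. One group size cannot give all three the same power under the same test, so if 15 per group is just enough for Rd at 90%, it is too few for the AUCs.

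What is at stake is how these secondary outcomes will be read after attrition. D4.1 analyses completers, and D2.3 withdraws participants who cannot keep to the extended schedule, so the analysed number may fall below 25 per group. A reader of D4.2 would infer that the AUC outcomes keep more than 90% power down to 15 per group, a loss of 10 per group. On the plan's own inputs they keep it only down to 20, a loss of 5. A null AUC result with 15 to 19 completers per group would then be given more weight than it deserves.

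**Working it through.** **Inputs (D4.2).** n = 15 per group, equal allocation, two-sided α = 0.05. Differences and SDs are as listed above. The stated SD is used directly, as D4.2 says, and taken as equal in both groups.

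**Formula.** Two-sample t-test for two means: standardised difference d = Δ/SD, degrees of freedom 2n − 2, noncentrality d·√(n/2), power from the noncentral t distribution.

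**Step 1: reproduce the plan's primary figure.** d = 7.9/6.4 = 1.234. At n = 15 the noncentrality is 1.234 × √7.5 = 3.38 on 28 df, and power is 90.4%. The difference detectable with exactly 90% power is 1.226 × 6.4 = 7.85, which agrees with the stated 7.9. The t-test at 15 per group and 90% power therefore fits the plan's own primary calculation.

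**Step 2: the same test for the AUCs.** Glucose: d = 137/130 = 1.054. Insulin: d = 90/85 = 1.059.

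| n per group | Glucose AUC power | Insulin AUC power |
|---|---|---|
| 15 | 79.6% | 79.9% |
| 19 | 88.5% | 88.8% |
| 20 | 90.1% | 90.4% |
| 22 | 92.7% | 92.9% |
| 23 | 93.8% | 94.0% |
| 25 | 95.5% | 95.6% |

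**Step 3: which settings do 137 and 90 fit?**

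| Setting | Detectable d | Glucose (× 130) | Insulin (× 85) |
|---|---|---|---|
| n = 15, 90% power | 1.226 | 159.4 (6.0% of 2650) | 104.2 (12.7% of 818) |
| n = 15, 80% power | 1.060 | 137.8 | 90.1 |
| n = 20, 90% power | 1.052 | 136.8 | 89.4 |

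The stated differences fit either of the last two rows, and not the first. The documents do not show which was intended.

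**Step 4: rounding.** The largest differences that still round to 5.2% and 11% are about 0.0525 × 2650 = 139.1 and 0.115 × 818 = 94.1. With the smallest SDs that round to 130 and 85 (129.5 and 84.5), power at 15 per group is about 81% and 84%.

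**Step 5: the planned ANCOVA.** Assume 130 and 85 are SDs of the difference between two days and that the variance is the same at both visits. The residual SD is then SD·√((1 + ρ)/2), on 2n − 3 df, where ρ is the baseline correlation.

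- *Insulin.* The plan's own figures give ρ = 1 − 85²/(2 × 333²) = 0.967, so the residual SD is 85 × 0.992 = 84.3. Power is 80.5% at 15, 89.2% at 19 and 90.8% at 20 per group. The difference detectable with 90% power at 15 per group is 103.5.
- *Glucose.* No ρ can be derived, so a range is assumed:

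| Assumed ρ | Power at 15/group | n/group for 90% | 90% detectable at 15/group |
|---|---|---|---|
| 0.5 | 89.5% | 16 | 138 |
| 0.7 | 85.5% | 18 | 147 |
| 0.9 | 81.4% | 20 | 156 |

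On this model, glucose reaches 90% at 15 per group only if ρ is below about 0.47.

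**Step 6: gene expression.** No arithmetic is needed. A claim of at least 80% power for one listed secondary outcome does not support a claim of more than 90% for all of them.

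**The case against.** Four points can be made for the plan.

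*The 90% claim may not be attached to 137 and 90.* It could refer to the literature effects cited alongside, which are larger. The smallest, 7.4% of 2650 = 196 mg/dl/24h, is 1.51 SD and has 97.9% power at 15 per group. On that reading the fault is only that 137 and 90 carry no group size or power. This does not succeed. The general sentence covers every listed outcome, the Rd difference is the 90%-power value at 15 per group, and the cited effects are for a 10-hour or breakfast window, not 24 hours.

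*ANCOVA may supply the missing power.* This stands in part for glucose, where a low enough correlation would do it, but D4.2 states none. If 130 and 85 are instead read as ordinary SDs of the outcome, power rises with correlation and passes 90% a little above 0.5 (at 0.6: 93.5% and 93.7%). For insulin that reading conflicts with the stated between-person SD of 333. The ANCOVA figures rest on assumptions and are less certain than the t-test result.

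*The practical effect is small.* This stands. At 25 per group both differences have over 95% power, and the 10-per-group margin is an inference, since D4.2 states no margin.

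*The gene-expression paragraph is a specific statement that qualifies the general one.* This is fair: if the 30% variance is read as an SD, 35/30 has 86.9% power at 15 per group, which agrees with its own claim. Only the word covering all outcomes is wrong.

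**Conclusion.** The concern holds. By the test that reproduces the primary outcome, 15 per group gives about 80% power for the stated glucose and insulin AUC differences, some 10 percentage points below the claim, and 20 per group are needed for 90%. The t-test result rests only on D4.2's own inputs, and rounding does not close the gap. The planned ANCOVA does not restore the joint claim: insulin still needs 20 per group under the assumptions shown, and glucose depends on a correlation that the documents do not give.

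The consequence is limited to the stated precision of two secondary outcomes and the scope of one sentence. The primary outcome is correct and the trial is not underpowered for these differences. If the retention above 90% reported for earlier studies in D7.3 holds here (25 × 0.9 = 22.5, so 22–23 completers per group), AUC power is 93–94%. The plan should be corrected, but its design need not change.

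**What to change.** Restate D4.2 in one of two ways, naming the test used:

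1. 15 per group gives 90% power for Rd (7.9, 13%) and about 80% power for 24-h glucose AUC (137, 5.2%) and 24-h insulin AUC (90, 11%); 90% power for those AUC differences needs 20 completers per group (two-sample t-test).
2. Keep 15 per group at 90% power and quote about 159 mg/dl/24h (6.0%) for glucose AUC and 104 µU/ml/24h (12.7%) for insulin AUC.

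If the glucose figure is to rest on ANCOVA instead, give the assumed baseline correlation. In either version, reword the general sentence so that it does not cover the molecular outcomes, and leave their statement of at least 80% power as it is.

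It would also help to add the 90%-power detectable differences at the planned 25 per group. By the same t-test, d = 0.936, which gives about 122 mg/dl/24h and 80 µU/ml/24h.

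The cost is a text change: no extra participants and no change to 25 per group. The price is that the precision stated at 15 per group becomes less favourable, either as lower power or as larger detectable differences.
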